3.1 Fracture and Retention

No loss of retention or fracture was observed in any restoration at baseline and 6-month follow-up. After the 18-month follow-up, 4 of the EFHT restorations (1 in class I or V and 2 in class II) were lost, and 1 (class II) was fractured (Table 3). Only one of the CR restorations (class II) was lost (Table 4). No loss of retention or fracture was observed in the SF2 restorations (Table 5). The type of cavity did not affect the performance of the restorative materials used ($p > 0.05$). EFHT (94.2%) showed significantly lower retention than SF2 (100%) after 18 months ($p = 0.019$), regardless of cavity type (Table 6). More restoration failures (de-bonding and fracture) were observed in class II cavities (4.4%) regardless of restorative material (Table 6), with no significant differences ($p = 0.26$). The Kaplan-Meier test presented significant differences among the survival rates of restorative materials over 18 months (Figure 2). The overall survival rates were 94.2% for EFHT, 98.8% for CR, and 100% for SF2 after 18 months.

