One qualified clinician assessed the restorations using a mirror and probe under a reflector light. He examined ten photos representing possible scores for each criterion before clinical evaluation. The postoperative sensitivity of the participants was evaluated by asking whether they had any pain throughout this period. Bite-wing and periapical radiographs were taken at 6- and 18-month evaluation periods. Periapical lesions, secondary caries, and compatibility with adjacent teeth were checked.

Statistical Analysis

Chi-square and Fisher Exact tests were performed to assess differences between restorative materials. Friedman and Wilcoxon Signed rank tests were performed to assess the effect of time on the restorations. Kaplan-Meier and Long-rank tests were also performed to determine the overall survival rates of the restorations. Survival rates were estimated by time to failure (4 or 5 scores) during clinical evaluation, regardless of color match and translucency criteria. The significance level was set at 0.05. The data was analyzed using statistical software (IBM SPSS 27.0; Chicago, IL, USA).

Results

A clinical flow diagram presenting the recruitment of participants is presented in Figure 1. Fourteen patients out of 160 did not meet the inclusion criteria and were excluded. One hundred forty-six patients (62 males and 84 females) were chosen, with a mean age of 28 (18-62). Initially, all patients participated (100%), but the participation rate fell to 89% in the 6-month evaluation. The participation rate further decreased to 79.4% in the 18-month evaluation. Finally, the last participation involved 116 patients, with 267 restorations being evaluated.

Table 2 displays the distribution of restorations based on jaws. Of the restorations, 59.9% (160) were placed in molars, and 40.1% (107) were placed in premolars. In terms of location, 48.3% (129) of the restorations were in the maxilla, and 51.6% (138) were in the mandible.

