3.5 Marginal and surface staining

No surface staining was observed in any restorative material over time (Figure 3). No marginal discoloration was observed in any restorations at one week and 6-month follow-ups. During the

18-month follow-up, only 1 (3.2%) restoration showed minor marginal staining in the class II EFHT group (Table 3).

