3.7 Anatomic form

There were no significant differences in anatomical form between the materials at baseline and during all evaluations ($p > 0.05$), regardless of cavity type. Furthermore, no significant difference was found between the initial measurements and later recalls for any of the materials ($p > 0.05$) (Tables 3-5). After 18 months, achieving proper anatomical form was significantly more difficult in class I and II cavities compared to class V (Table 6 and Figure 3) ($p = 0.002$), regardless of restorative material type.

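### Section 3.1 concludes that cavity type had no effect on the strength of p > 0.05 alone, although six failures leave the question open

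*Protocol*

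**What the plan says.** Section 3.1 of the Protocol (Fracture and Retention) lists the 18-month failures by material and cavity class. For EFHT, "4 of the EFHT restorations (1 in class I or V and 2 in class II) were lost, and 1 (class II) was fractured". For ChemFill Rock (CR), "Only one of the CR restorations (class II) was lost". For SonicFill 2 (SF2), "No loss of retention or fracture was observed in the SF2 restorations".

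The section then concludes "The type of cavity did not affect the performance of the restorative materials used", with p > 0.05 in brackets and nothing else in support.

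Two sentences later it returns to cavity class with all materials pooled: "More restoration failures (de-bonding and fracture) were observed in class II cavities (4.4%) regardless of restorative material". It cites Table 6 and adds that the difference was not significant, p = 0.26.

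The start of the Results section gives the 18-month base: "the last participation involved 116 patients, with 267 restorations being evaluated". The text gives no confidence interval, equivalence margin or power for the comparison between cavity classes.

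**The concern.** A p-value above 0.05 means that the test did not detect a difference. Concluding that there is none needs an interval narrow enough to rule out differences that matter, and the text offers no such interval. With six failures in 267 restorations, any interval for a class contrast will be wide.

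The two statements on cavity class in section 3.1 differ in strength. The pooled statement gives a direction, a rate and a p-value, and says only that the difference was not significant. The other asserts no effect, comes first, and can be quoted on its own. Class I, II and V lesions were all eligible, so readers will want to know whether class matters for retention. The sentence tells them that it does not, when the data have not settled the question.

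**Working it through.** **Inputs**
- Failures (section 3.1): EFHT 4 lost and 1 fractured, CR 1 lost, SF2 none. Total 4 + 1 + 1 + 0 = 6.
- Class of the EFHT losses: the count of 1 given jointly for classes I and V must mean one in each, because only 1 + 1 + 2 adds to the 4 reported lost.
- Class II failures: 2 EFHT lost + 1 EFHT fractured + 1 CR lost = 4. Elsewhere: 2.
- Base: 267 restorations in 116 patients (Results), taken as the 18-month denominator.

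**Reproducing the reported 4.4%.** 4/90 = 4.44% and 4/91 = 4.40% both round to 4.4%; 4/89 = 4.49% and 4/92 = 4.35% do not fit as well, rounding to 4.5% and 4.3%. Class II therefore held 90 or 91 restorations, leaving 177 or 176 in the other classes. This agrees with the four-to-two split.

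**Reproducing p = 0.26.** Take a three-class likelihood-ratio test with 4, 1 and 1 failures. Class II is 91, and classes I and V are assumed to be 88 each, since their true sizes are not in the text shown.
- Expected failures: 6 × 91/267 = 2.045 and 6 × 88/267 = 1.978 (twice). Expected non-failures: 88.955 and 86.022 (twice).
- G² = 2 × [4 ln(4/2.045) + 2 ln(1/1.978) + 87 ln(87/88.955) + 2 × 87 ln(87/86.022)] ≈ 2.70 on 2 df, so p = exp(-2.70/2) ≈ 0.26.
- Letting class I range from 70 to 105 gives 0.25 to 0.26.

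The reported value is therefore attainable, and it need not equal the two-group Fisher value below.

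**Pooled contrast, class II against the rest (4/91 v 2/176)**
- Rates: 4.40% and 1.14%. Difference 3.26 points. Risk ratio 4.40/1.14 = 3.87.
- Wilson 95% limits: 1.72% to 10.76% for class II; 0.31% to 4.05% for the rest.
- Newcombe interval for the difference:
  - lower = 3.26 - √[(4.40 - 1.72)² + (4.05 - 1.14)²] = -0.69
  - upper = 3.26 + √[(10.76 - 4.40)² + (1.14 - 0.31)²] = 9.68
- Score (Koopman) interval for the risk ratio: all R for which |p₁ - R·p₂| divided by its standard error, taken at the constrained maximum-likelihood estimates, is at most 1.96. Result: 0.84 to 17.8.
- Fisher exact p = 0.18.
- With 4/90 v 2/177: risk ratio 3.93 (0.86 to 18.1), difference 3.3 points (-0.6 to 9.8).

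**EFHT alone (3/31 v 2/55)**
- EFHT total: 5 failures at 94.2% retention gives 86 only (1 - 5/86 = 94.19%).
- EFHT class II: section 3.5 reports "only 1 (3.2%) restoration showed minor marginal staining in the class II EFHT group", and 1/31 = 3.23% is the only fit. Others: 86 - 31 = 55.
- Rates 9.68% and 3.64%. Difference 6.04 points (Newcombe -4.71 to 21.49). Risk ratio 2.66 (score 0.55 to 12.8). Fisher p = 0.35.
- If the 31 leaves out the three failed restorations: 3/34 v 2/52, risk ratio 2.29 (0.48 to 11.0).
- CR has one failure and SF2 none, so neither can show that class makes no difference.

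**Sensitivity to the split.** Fisher p for six failures, class II to others: 4:2 gives 0.185, 5:1 gives 0.019, 6:0 gives 0.001. Moving one failure to class II would have changed the answer.

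**Clustering.** Mean restorations per patient: 267/116 = 2.30. Assume a within-patient correlation of 0.05 to 0.3 and one cavity class per patient, the worst case. The design effect 1 + (2.30 - 1) × ICC is then 1.07 to 1.39. The pooled risk-ratio interval widens to between 0.81–18.5 and 0.67–22.2, and the difference to between -0.8 to 10.0 and -1.5 to 11.3 points.

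**The case against.** The best defence is that section 3.1 supplies most of the correction itself. It lists every failure by material and class, says that class II had more, gives the rate and p = 0.26, and there speaks only of no significant difference. A reader of the whole paragraph is not misled about direction. This stands, and it reduces the point to one over-worded sentence.

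It can also be said that the quoted sentence follows the results for each material, so its p-value may come from tests within materials. The pooled four-to-two split would then belong to the later sentence, which is properly worded. The text does not settle this, so both readings are worked above. The objection does not rescue the claim, because three against two within EFHT is less informative than the pooled split.

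The denominators are reconstructed from rounded percentages, so the intervals are illustrative. The conclusion does not hang on them: six failures are too few to establish absence of effect under any plausible class totals.

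A reader might also infer that the sentence contradicts section 3.7, where "achieving proper anatomical form was significantly more difficult in class I and II cavities compared to class V" (p = 0.002). The documents do not support that. The sentence stands under the Fracture and Retention heading, straight after the failure counts, and anatomic form has its own section and test.

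**Conclusion.** The statement that cavity type had no effect is not supported. The pooled estimate is a risk ratio of 3.9 (95% CI 0.8 to 18) and a difference of 3.3 points (-0.7 to 9.7). Within EFHT the ratio is 2.7 (0.6 to 13). Both sets of intervals include no difference, a slightly lower rate in class II and a rate several times higher.

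This rests on four assumptions: one EFHT loss in each of classes I and V, 267 as the 18-month denominator, class sizes recovered from percentages, and independent restorations. Positive correlation within patients would widen the intervals further. The EFHT figures are the less certain, because their class II denominator comes from a staining percentage.

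Two stronger readings should be resisted. One is that class II cavities do fail more often: the intervals include no difference, and the Protocol claims no such effect. The other is that p = 0.26 is wrong because a two-group Fisher test gives 0.18: a three-class test reproduces 0.26. The comparisons between materials and the survival rates are untouched. Severity is minor.

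**What to change.** Replace the sentence with: *No significant difference in retention or fracture between cavity classes was detected; with only six failures the data are inconclusive and are compatible with no difference as well as with a several-fold higher failure rate in class II.*

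State whether the accompanying p > 0.05 is a pooled test or one for each material. Give the failure counts and denominators by cavity class, with 95% confidence intervals for the class comparison calculated from the actual data in place of the back-calculated figures used here. Intervals that allow for several restorations in one patient would be better still.

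The cost is one reworded sentence and a few intervals from data already held. The only drawback is a slightly less favourable conclusion.

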3.4 Color match and translucency

The color match between teeth and the materials differed significantly for restorative materials ($p < 0.001$, Tables 3-5). The color and translucency of EFHT restorations matched the teeth better compared to CR restorations ($p < 0.001$) but were worse than SF2 restorations ($p < 0.001$, Table 6, and Figure 3).

3.5 Marginal and surface staining

No surface staining was observed in any restorative material over time (Figure 3). No marginal discoloration was observed in any restorations at one week and 6-month follow-ups. During the

18-month follow-up, only 1 (3.2%) restoration showed minor marginal staining in the class II EFHT group (Table 3).

3.6 Marginal adaptation

No deterioration in marginal adaptation was observed in any restorations during the 18-month follow-up (Figure 3). Only 1 (3.2%) restoration for EFHT in the class II cavity showed slight marginal discrepancies after an 18-month follow-up (Table 3).

3.7 Anatomic form

There were no significant differences in anatomical form between the materials at baseline and during all evaluations ($p > 0.05$), regardless of cavity type. Furthermore, no significant difference was found between the initial measurements and later recalls for any of the materials ($p > 0.05$) (Tables 3-5). After 18 months, achieving proper anatomical form was significantly more difficult in class I and II cavities compared to class V (Table 6 and Figure 3) ($p = 0.002$), regardless of restorative material type.

3.8 Postoperative Sensitivity

No postoperative sensitivity was observed in the EFHT and CR restorations during the 18-month follow-up. Only three restorations for SF2 in the class I cavities showed slight postoperative sensitivity at one week (7.5%), with no significant differences when compared to other times ($p > 0.05$) or when compared to other cavities ($p = 0.269$) (Table 5). This postoperative sensitivity disappeared over time.

3.9 Secondary Caries

No secondary caries were seen in any restorations during the 18-month follow-up.
